#### **Version history**:

Version:	Date:	Changes:		
0.1	20/04/2020	First draft of SAP		
0.2	21/04/2020	Additional analysis code added		
0.3	24/04/2020	Additional details on outcomes scoring added.		
0.4	05/05/2020	Additional details on outcomes scoring added. Description of analysis of health economic data added.		
0.5	22/06/2020	Analysis of outcomes relating to cannabis use restricted to cannabis users at baseline.  Partially missing data in primary outcome due to telephone completion (items n1, g4, g5) to be prorated.  Inferential analysis of TLFB to be carried out at both 1 month and three months (previously was 3 months only).  A criteria for conducting a sensitivity analysis looking at the impact of COVID-19 on outcomes has been added.  Subgroup analysis comparing treatment effect for different versions of the app has been added.  Reverse scoring of some items of IMSI added to derivation of outcomes  Reverse scoring of some items of ERS added to derivation of outcomes.		
1.0	29/06/20	Signed version circulated		

#### **Quantitative Analysis Plan**

This document details the presentation and analysis strategy for the primary papers reporting results from the Actissist 2.0 trial. It is intended that the results reported in these papers will follow the strategy set out herein; subsequent papers of a more exploratory nature will not be bound by this analysis plan but will be expected to follow the broad principles laid down for the primary paper(s). The principles are not intended to curtail exploratory analysis or to prohibit sensible statistical and reporting practices but they are intended to establish the strategy that will be followed as closely as possible in analysing and reporting the trial.

Health economic outcomes are addressed briefly however this plan does not include a health economic analysis.

## 1. Brief description of the trial

#### **Trial design**

Actissist is a parallel-group randomised controlled trial, with 1:1 allocation and blinded assessors, to test the efficacy of the Actissist intervention in reducing severity of symptoms in people with psychosis when added to Treatment as usual (TAU), compared with routine symptom monitoring plus TAU.

#### Sample size

The planned sample size was 170 participants recruited over 19 months. 63 per group will give 80% power to detect an effect size of 0.4 (6 points on the PANSS with an SD of 15), based on a two-group t-test with a 0.05 two-sided significance level, assuming a baseline-endpoint correlation of 0.6. Allowing 20% loss to follow-up, in order to maintain 80% power, we will recruit 85 patients per group (N=170). The SD, correlation and attrition rate are based on figures from Actissist 1.0.

### Randomisation procedure, allocation concealment

The randomisation process is conducted by a remote internet-based randomisation service (www.sealedenvelope.com). The allocation sequence will be developed using a computer random number generator to allocate participants on a 1:1 ratio, stratified by service (early intervention vs community mental health).

The randomisation list will be kept by the remote randomisation service (www.sealedenvelope.com) and kept separate to the collection of outcomes on the study database. The randomisation list will only be revealed to the researchers once all the recruitment is completed.

#### Blinding

The assessment of the primary outcome will be blinded. Blindness of raters is ensured using a variety of procedures, including briefing participants prior to assessment not to disclose their allocation and data protection of randomisation information. RAs will remain blind to group allocation. An RA who did not conduct the phone set up session will conduct the follow up assessment to maintain the blind. The project officer, or a member of the research team independent to the follow up procedure, will book follow up appointments to further ensure blinding is maintained. Unblindings will be regularly monitored and recorded. Deliberate unblinding would only occur in the case of a serious adverse incident such as risk towards self/others by a participant. The trial statisticians will be partially blinded during the analysis by withholding the identity of the randomised groups and only once the analysis is completed and interpreted will these be revealed. Due to the nature of the intervention, all participants will be unblinded and fully aware of their allocation to the intervention or control groups.

#### **Eligibility screening**

#### Inclusion criteria:

- i). Either:
- 1) Meet ICD-10 criteria for a schizophrenia-spectrum diagnosis (ICD codes F20, F22, F23, F25, F28, F29) as confirmed by the treating clinician;

OR

- 2) Meet the early Intervention for Psychosis Service entry criteria, operationally defined using the Positive and Negative Syndrome Scale (PANSS) and/or the psychosis transition criteria of the Comprehensive Assessment of At-Risk Mental States (CAARMS);
- ii) in contact with mental health services;
- iii) within 5 years from onset of first psychotic episode, deemed by the treating clinician;
- iv) meet a criterion level of positive symptoms severity, indicated by a score of >3 (symptom present) on any PANSS positive item and a score of >3 (symptom present) on any PANSS negative or PANSS general items;
- v) English speaking;
- vi) aged 16 years or older;
- vii) capacity and willingness to provide informed consent;
- viii) not currently participating in another trial.

#### Exclusion criteria:

- i) Anyone with psychosis not in contact with a NHS mental health service.
- ii. Anyone less than 16 years old at the point of recruitment.
- iii) Anyone not capable of giving informed consent.
- iv) Non-English proficient.
- v) Score <3 on all PANSS positive, negative and general items.

### 2. Outcome measures

## **Primary outcome**

The primary outcome is psychotic symptoms measured by PANSS total score at 12 weeks post randomisation(1).

#### **Secondary outcomes**

At 24 weeks randomisation:

1. 1. Psychotic symptoms measured using PANSS total score (1)

At 12 weeks post randomisation and 24 weeks post randomisation:

- 1. Symptom distress measured using:
  - i. Psychotic Symptoms Rating Scales (PSYRATS) delusions subscale (2)
  - ii. PSYRATS hallucinations subscale (2)
- 2. Mood measured using the Calgary Depression Scale (CDSS) for Schizophrenia (3)
- 3. Social functioning measured using the Personal and Social Performance Scale total score (PSP) (4)
- 4. Perceived criticism and warmth measured using:
  - i. Perceived Criticism and Perceived Warmth Scale (PCPW) perceived criticism subscale (5)
  - ii. PCPW perceived warmth subscale (5)
- 5. Recovery is measured using the Questionnaire about the Process of Recovery (QPR) (6)
- 6. Well-being is measured using the Warwick-Edinburgh Mental Wellbeing Scale (WEMWEBS) (7, 8)
- 7. Internalised stigma is measured using the Internalised Stigma of Mental Illness Inventory (ISMI) (9)
- 8. Substance use measured using:
  - i. The Alcohol Use Disorders Inventory (AUDIT; past 3 months) (10, 11)
  - ii. Cannabis Use Disorders Inventory-Revised (CUDIT-R; past 3 months) (12)
  - iii. Alcohol, Smoking and Substance Involvement Screening Test (ASSIST) (13)
    - Separate scores for: tobacco, alcohol, cannabis, cocaine, amphetamine type simulants, inhalants, sedatives, hallucinogens, opiods, and other drugs
  - iv. Three subscales of the Drug Use Disorder Identification Test-Extended cannabis only (DUDIT-e) (14):
    - Positive aspects
    - Negative aspects
    - Treatment readiness
  - v. Cannabis use in the last month, and last 3 months measured using the Time Line Follow Back for drugs and alcohol (TLFB). We will analyse two outcomes from this data (15, 16):
    - Proportion of days using cannabis
    - Average daily weight per cannabis using day
- 9. Empowerment is measured using the Empowerment Scale (ERS) (17)

#### **App Engagement**

- 1. App engagement is measured at 12 weeks using the Quantitative Feedback Questionnaire (QFQ) aggregated into four subscales:
  - i. Ease of use
  - ii. Fit in daily life
  - iii. Acceptability
  - iv. Perceived helpfulness

### **Health economic outcomes**

1. Quality of life measured using Euro-Qol Five Dimension (EQ-5D-5L) Service utilisation, income, accommodation and other cost-related variables measured using the Client Service Receipt Inventory (CSRI).

## 4. Data summary and reporting

Descriptive statistics within each randomised group will be presented for baseline values. These will include counts and percentages for binary and categorical variables, and means and standard deviations, or medians with lower and upper quartiles, for continuous variables, along with counts of missing values. There will be no tests of statistical significance or confidence intervals for differences between randomised groups on any baseline variable.

Descriptive statistics will be used to summarize drop-out and completeness of therapy.

Outcomes at 12 and 24 weeks will be presented separately for each group and summarised using means and standard deviations, along with counts of missing values.

The number of serious adverse events and adverse events will be presented as the number of events and number of individuals with events. These will be provided separately for each randomised group.

## 5. Statistical methods for inferential analysis

#### Analysis of primary and secondary outcomes

The primary and secondary outcomes, with the exception of the proportion of cannabis free days, will be analysed using a linear mixed-effects models with outcome measurement (at the two follow-up time points) as the dependant variable. The model will include fixed effects for timepoint, treatment, timepoint by treatment interactions, the baseline measure of the outcome, assuming a linear relationship between baseline and outcome, and service (2 categories: i) early intervention; ii) community mental health). Observations will be clustered by participant with an unstructured correlation matrix for the residuals. The model will be fitted using restricted maximum likelihood (19).

For each outcome and timepoint we will report the treatment effect estimate as the adjusted mean difference between groups, its standard error, 95% confidence intervals and p-value.

In addition, we will report estimates for Cohen's D effect sizes as the adjusted mean difference of the outcome divided by the sample standard deviation of the outcome at baseline. Confidence intervals for Cohen's D will be calculated by dividing the confidence limits by the sample standard deviation of the outcome at baseline. These will be displayed in a Forest Plot with the primary outcome at the top, followed by secondary outcomes.

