#### Assumptions for primary analysis

The primary analysis assumes data are missing at random, conditional on the observed values of the outcome at baseline, and follow up, and other covariates in the model.

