#### Sensitivity analysis

We will conduct a sensitivity analysis for the primary outcome to assess whether different assumptions about missing data lead to different results. The sensitivity analysis will be conducted using the same model as is used in the primary analysis with the addition of baseline variables found to be predictive of missingness. Baseline variables will be considered predictive of missingness if p < 0.05 in a univariate logistic regression model, with attending the visit as the outcome and the baseline variable of interest as the only predictor. This sensitivity analysis will assume data is missing at random conditional on the variables in the primary analysis model and variables that are found to be predictive of missingness.

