#### Analysis code

\*Model for outcomes analysed using mixed effect model:

```
mixed outcome i.treat##i.timepoint baseline service || pid:, ///
res(unstructured, t(timepoint)) noconstant reml
margins treat, at(timepoint==12) pwcompare(effects)
```

\*Model for proportion of abstinent days from timeline follow back:

```
meglm outcome i.treat##i.timepoint baseline service || pid:, ///
res(unstructured, t(timepoint)) noconstant ///
family(binomial 30) link(identity)
```

\*\*End of treatment - should be the same as main effect of treat in above command

```
**Follow-up
```

```
margins treat, at(timepoint==24) pwcompare(effects)

//Should be the same as main effect of treat in:

// mixed outcome i.treat##ib24.timepoint baseline service || pid:, ///
res(unstructured, t(timepoint)) noconstant reml
```

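### The mixed model gives baseline one slope for both 12 and 24 weeks; if the true slopes differ and dropout depends on baseline differently by arm, the 24-week estimate is modestly biased, and a baseline-by-timepoint term prevents this at almost no cost

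*SAP*

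**What the plan says.** Under 'Analysis of primary and secondary outcomes', the SAP states: "The model will include fixed effects for timepoint, treatment, timepoint by treatment interactions", followed by "the baseline measure of the outcome, assuming a linear relationship between baseline and outcome" and service. The only interaction is treatment by timepoint. Appendix 1 agrees: "mixed outcome i.treat##i.timepoint baseline service || pid" crosses treatment with timepoint and leaves baseline as a main effect.

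On the covariance, "Observations will be clustered by participant with an unstructured correlation matrix for the residuals". On missing data, "The primary analysis assumes data are missing at random, conditional on the observed values of the outcome at baseline, and follow up, and other covariates"; treatment is one of those covariates. The missing-data sensitivity analysis is run "using the same model as is used in the primary analysis with the addition of baseline variables found to be predictive of missingness".

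The time point of main interest is 12 weeks: "The primary outcome is psychotic symptoms measured by PANSS total score at 12 weeks post randomisation". PANSS at 24 weeks is secondary, but the SAP commits to an estimate, confidence interval and p-value for every outcome at each time point.

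**The concern.** The model lets the treatment effect, the residual variances and their covariance vary by visit, but holds the baseline relation equal at 12 and 24 weeks and gives no reason. The unstructured residual matrix does not relax this, because it describes covariance and not the mean.

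A likelihood analysis is protected under missing at random only if the mean model is right at each visit. Suppose the slopes differ, and the participants still assessed at 24 weeks differ in baseline severity between arms because dropout related to baseline differently in each arm. A common slope then corrects that imbalance by the wrong amount. The stated missing-at-random condition covers such dropout, since both baseline and treatment are in the model.

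The sensitivity analysis adds covariates but keeps the shared slope, so it would not remove the bias. At stake are the 24-week estimates for the outcomes in the linear mixed model, and for the EQ-5D visual analogue scale, which is analysed in the same way.

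**Working it through.** **Inputs from the SAP (Sample size).** Difference 6 points, SD 15, baseline-endpoint correlation 0.6 (a single value, not given by visit), two-sided 0.05, 80% power, 20% loss, N = 170.

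**The plan's own figure.** Adjusted SD = 15 × √(1 − 0.6²) = 12. n per group = 2 × (1.960 + 0.842)² × (12/6)² = 62.8, so 63. This reproduces the SAP, and the same SD and correlation are used below.

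**Assumptions not in the SAP.** 12-week slope 0.6; 24-week slope 0.6, 0.5, 0.4 or 0.3; residual correlation between visits 0.4 or 0.6; 20% missing at 24 weeks and 10% at 12 weeks; log-odds of dropout changing by 0, 0.5 or 1 per baseline SD, in opposite directions by arm or in one arm only. Service is left out.

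**The common slope.** With complete data it is a weighted mean of the two visit slopes, with weight on 12 weeks w = (v24 − c)/(v12 + v24 − 2c), where v12 and v24 are the residual variances and c their covariance. For a 24-week slope of 0.4 and residual correlation 0.4:
- v12 = 225 × (1 − 0.36) = 144; v24 = 225 × (1 − 0.16) = 189; c = 0.4 × √(144 × 189) = 66.0
- w = 123.0/201.0 = 0.61
- common slope = 0.61 × 0.6 + 0.39 × 0.4 = 0.52 (0.53 when fitted with the missing data)

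The slope is then too low at 12 weeks and too high at 24 weeks.

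**Approximate 24-week bias.** Bias ≈ (true 24-week slope − common slope) × baseline gap between arms among those assessed. With strong opposite dropout the gap is −5.25 points, so (0.40 − 0.53) × (−5.25) = +0.68. The full fit gives 0.75, because it also borrows from the 12-week residuals of those who left.

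**Large-sample fits of the planned model, 20% missing at 24 weeks** (bias in PANSS points, rounded, across the dropout patterns and residual correlations):

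| 24-week slope | Bias at 24 weeks, planned model | With baseline by timepoint |
|---|---|---|
| 0.6 (equal) | 0 | 0 |
| 0.5 | 0.1 to 0.35 | 0 |
| 0.4 | 0.3 to 0.9 | 0 |
| 0.3 | 0.35 to 1.3 | 0 |

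Zero means within simulation error, at most about 0.08 points. The lower ends come from dependence in one arm only, the upper ends from strong dependence in opposite directions. The sign follows the direction of the dropout. With unequal slopes but dropout unrelated to baseline, the bias is again zero. At 12 weeks it is usually 0.1 to 0.2 points, and at most about 0.35 in any scenario, including stress cases with 30% missing.

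**Precision at N = 170** (1,500 replicates, dropout unrelated to baseline; standard error of the 24-week effect):

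| 24-week slope | Planned model | With baseline by timepoint |
|---|---|---|
| 0.6 | 1.94 | 1.94 |
| 0.4 | 2.30 | 2.29 |
| 0.3 | 2.56 | 2.47 |

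The interaction costs nothing visible when the slopes are equal and gains up to about 4% of the standard error when they are not (2.56/2.47 = 1.04).

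**The case against.** The common slope is a coherent, openly stated and parsimonious choice, and the text and code agree, so nothing is contradicted. The SAP gives one correlation and no evidence that the slopes differ by visit. Bias needs two conditions together: unequal slopes, and dropout that depends on baseline differently by arm. The SAP shows neither. The larger figures come from dropout running in opposite directions in the two arms, which is a demanding pattern. Even then the bias at the planned 20% loss is no more than about half a standard error (1.3/2.5 = 0.52), and it falls on a secondary time point.

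All of this stands, and it sets the weight of the point. A reader might infer that baseline is in fact mis-adjusted at each visit, or that arm-differential dropout is enough to bias the 24-week effect. Neither follows: with equal slopes the planned model is unbiased even under strong arm-differential dropout. Chance baseline imbalance alone costs only precision, because randomisation keeps the estimate unbiased.

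What the objection does not remove is that the SAP's missing-data assumption covers a situation its mean model may not handle, and that closing the gap is nearly free.

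**Conclusion.** The point holds as a minor, conditional weakness of specification. If the baseline slopes differ between visits and dropout depends on baseline differently by arm, the planned model biases the 24-week PANSS effect by roughly 0.1 to 0.35, 0.3 to 0.9 or 0.35 to 1.3 points for assumed 24-week slopes of 0.5, 0.4 or 0.3. The planned difference is 6 points and the 24-week standard error is about 1.9 to 2.6. Stress cases go higher: 30% missing with strong opposite dependence gives 0.5 to 2.0 points, and an extreme pair of slopes (0.7 and 0.3) reaches about 2.7. These go beyond the planned loss or the planned correlation.

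It would be tempting to conclude that the primary analysis is compromised. The figures do not support that: the 12-week bias is at most about 0.35 points, or 0.35/6 = 6% of the planned difference. The slopes by visit, the dropout patterns and the residual correlations are all assumptions; the SD, the 0.6 correlation and the 20% loss are the SAP's own.

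**What to change.** - In 'Analysis of primary and secondary outcomes', add a baseline-by-timepoint interaction to the listed fixed effects.
- In Appendix 1, change the fixed part of the `mixed` command to `i.treat##i.timepoint c.baseline##i.timepoint service`. Change the commented 24-week check line to match: `i.treat##ib24.timepoint c.baseline##ib24.timepoint service`. The `margins` commands need no change.
- Carry the term into the EQ-5D visual analogue scale model and the missing-data sensitivity analysis.
- The 'Time line follow back (TLFB)' section gives the binomial model the same fixed part. Either add the term to the `meglm` code or state there that this model keeps baseline as a main effect only; otherwise text and code will disagree.

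The cost is one extra parameter per outcome and a few words of text. For PANSS at N = 170 precision is essentially unchanged; the cannabis-user subset was not examined. The term should be prespecified, not added after the slopes have been seen.

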#### Time line follow back (TLFB)

Average weight per using day will be analysed using a linear mixed-effects model in the same way as other primary and secondary outcomes.

The proportion of cannabis free days will be analysed using a mixed effects generalised linear model, with family binomial and an identity link. The random and fixed parts of the model will be specified in the same way as the mixed effects model for other primary and secondary outcomes, including the baseline proportion of cannabis free days as a fixed effect.

Inferential analysis will only be conducted on outcomes from the TLFB separately for one month recall and three month recall (proportion of abstinent days and Average daily weight per cannabis using day).

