## Scoring rules for outcomes

Outcome acronym	Number of	Scoring	Min-Max	Scores for
Succome acronym	questions	Jeornig	possible	better
	questions		values	outcomes
PANSS total score	30 (7 +ve, 7 -	Sum of items	30-210	Lower
	ve, 16 general)			
PSYRATS - delusions	6	Sum of all items	0-24	Lower
PSYRATS - hallucination	11	Sum of all items	00-44	Lower
CDSS	9	Sum of items	0-27	Lower
PSP	4	Total score is entered directly into the database	1-100	Higher
PCPW – Perceived criticism	4	Mean of items	1-10	Lower
PCPW – Perceived warmth	3	Mean of items	1-10	Lower
QPR	15	Sum of the items	15-75	Higher
WEMWEBS	14	Sum of the items	14-70	Higher
ISMI	29	Mean of completed	1-4	Lower
		items reverse scoring items 7, 14, 24, 26 and 27		
AUDIT; past 3 months)	10	Sum of items	0-40	Lower
CUDIT-R; past 3 months.	8	Sum of items	0-32	Lower
ASSIST	71	Sum of items by substance.	0-31 tobacco 00-39 other drugs	Lower
DUDIT-e: Positive aspects	17	Sum of items	0-68	Higher scores more positive
DUDIT-e: Negative aspects	17	Sum of items	0-68	Higher scores more negative
DUDIT-e: Treatment 8 readiness		Sum of items excluding items 6 and 7 and reverse scoring items 1 and 9.	0-16	Higher scores more ready
TLFB – Proportion of days using cannabis*		Numerator: 30 – number of days abstinent Denominator: 30	0-1	Lower

TLFB - Average daily weight per cannabis using day*	2	Total weight/using days.  Total weight = number of units consumed.  Using days = (30 - number of days abstinent)  If using days = 0 outcome will be 0.	Non- negative	
ERS	28	Sum of the items. Reverse score items 10-18, and item 28.	28-112	Higher
QFQ - Ease of use	5	Qs 7, 8 (reversed), 11, 12 (reversed)	1-7	Lower
QFQ - Fit in daily life	5	Qs 3, 5, 6, 9, 10, and 21	1-7	Lower
QFQ - Acceptability	6	Qs 4, 15, 16, 17 (reversed), 20, 22 (reversed)	1-7	Lower
QFQ - Perceived helpfulness	4	Qs 13 (reversed), 14 (reversed), 18 and 19 (reversed)	1-7	Lower

\*One month recall data was collected using a 30 day period. For three month the time period was 90 days.

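### The binomial model for the TLFB cannabis proportion has no participant-level variance, so its standard errors would be too small; its number of trials and outcome direction also need reconciling

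*SAP*

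**What the plan says.** The linear model in SAP section 5 (Analysis of primary and secondary outcomes) handles repeated measures as follows: "Observations will be clustered by participant with an unstructured correlation matrix for the residuals". No random intercept is mentioned.

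The TLFB subsection makes an exception for one outcome: "The proportion of cannabis free days will be analysed using a mixed effects generalised linear model, with family binomial and an identity link". It then carries the structure over: "The random and fixed parts of the model will be specified in the same way as the mixed effects model". Inference is planned separately for one-month and three-month recall.

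The code in Appendix 1 follows the text. The command begins "meglm outcome i.treat##i.timepoint baseline service || pid", lists no random-effect variable after the participant identifier, requests an unstructured residual matrix over timepoints, sets `noconstant`, and ends with "family(binomial 30) link(identity". No 90-trial version is given, although the footnote to the scoring table in Appendix 2 reads: "For three month the time period was 90 days".

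Section 2 lists the outcome as "Proportion of days using cannabis", and Appendix 2 scores it that way with lower values better. Section 5 and the code comment in Appendix 1 refer instead to cannabis-free or abstinent days.

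**The concern.** A Gaussian model estimates its residual variances and covariance from the data, so between-person variation is absorbed there even without a random intercept. A binomial variance is fixed once the mean and the number of trials are known. Copying the Gaussian random part therefore leaves no parameter for differences between people. If software fits the model at all, it treats a person's 30 days as 30 independent observations, although someone who used cannabis yesterday is more likely than average to have used it today.

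At stake are the standard error, confidence interval and p-value that section 5 requires for this outcome at 12 and 24 weeks, for both recall periods. Intervals that are too narrow invite a false claim of an effect on cannabis use.

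**Working it through.** The SAP states no power, variance or standard error for any TLFB outcome, so there is no figure of its own to reproduce.

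**Inputs.** Days recalled, m = 30 or 90 (Appendix 2, footnote). Trials in the code, t = 30 (Appendix 1). Within-person correlation of days, rho: not in the SAP; 0.02 to 0.7 assumed. Number of baseline cannabis users: not in the SAP; 60 assumed in the main simulation.

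**Step 1: size of the understatement.** A participant's proportion has true variance p(1−p)/m × [1 + (m−1)rho]. The model without participant variance assigns p(1−p)/t. The ratio of true to model standard error is therefore

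sqrt{[1 + (m−1)rho] × t/m}.

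For m = t = 30 and rho = 0.1 this is sqrt(1 + 29 × 0.1) = sqrt(3.9) = 1.97.

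| rho | 30 days, 30 trials | 90 days, 30 trials (rescaled proportion) | 90 days, 90 trials |
|---|---|---|---|
| 0.02 | 1.26 | 0.96 | 1.67 |
| 0.1 | 1.97 | 1.82 | 3.15 |
| 0.3 | 3.11 | 3.04 | 5.26 |
| 0.5 | 3.94 | 3.89 | 6.75 |
| 0.7 | 4.62 | 4.59 | 7.96 |

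The implied type I error is 2[1 − Φ(1.96/ratio)]. For one month this gives about 12% at rho 0.02, 32% at 0.1, 53% at 0.3 and 62% at 0.5. Here rho is the correlation left after covariate adjustment; adjusting for baseline lowers it.

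**Step 2: simulation under no effect.** Beta-binomial counts with mean 0.5, 60 participants, two follow-ups, baseline and service as covariates, correlation over time 0.4 to 0.8, rho 0.1 to 0.7, 300 runs per setting, identity-link binomial fit without participant variance:

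- 30 days, 30 trials: ratio 1.6–1.9 at rho 0.1, 2.5–2.9 at 0.3, 3.2–3.7 at 0.5, 4.4–4.7 at 0.7; type I error 22–69%.
- 90 days, 30 trials on the rescaled proportion: ratio 1.3–4.6; type I error 14–66%.
- 90 days, 90 trials: ratio 2.2–8.6; type I error 38–83%.
- Same fits with participant-clustered standard errors: type I error about 3–14%.

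In a simpler setting (one follow-up, 40 or 60 users, baseline-adjusted), ordinary linear regression on the proportion gave 4–7%.

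**Step 3: the 30 trials.** Using 30 in place of 90 multiplies the model standard error by sqrt(90/30) = 1.73. This works against the first error: compare the last two columns of the table. If raw 90-day counts are entered instead, any value above 30 exceeds the number of trials and the model is undefined. The code does not say on which scale the three-month outcome would be entered.

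**Step 4: restoring a normal random intercept.** On the identity link, a person's probability is the mean plus a normal deviate with variance rho × p(1−p). At a mean of 0.5 the 0 and 1 limits lie 1/sqrt(rho) standard deviations away. The share of people placed outside 0–1 is 2[1 − Φ(1/sqrt(rho))]: about 0.2% at rho 0.1, 7% at 0.3 and 16% at 0.5.

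**Step 5: direction.** Proportion free = 1 − proportion using. The estimate changes sign; its size, standard error and p-value do not.

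**The case against.** The text names a mixed-effects model and clusters observations by participant, and Appendix 1 is headed as example code. The intent to allow for clustering is clear, and nothing shows that an unclustered fit would in fact be run and reported. That limits the conclusion to what follows if the model is fitted as written. It does not remove the defect: text and code agree on a random part that carries no variance in a binomial model, and no robust or overdispersion correction is stated.

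The size is also open. At rho 0.1 the one-month shortfall is no more than about 2-fold, and the SAP gives nothing from which to estimate rho. That stands.

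A reader might infer more than the documents support:

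- That the 30 trials help make the standard errors too small. They do the opposite for a rescaled 90-day proportion, and 30 is correct for one month.
- That the understatement exceeds 5-fold. Such figures belong to a 90-trial fit, which the code does not contain, or to no setting in the 30-trial columns.
- That many participants will sit at 0 or 30 days. The SAP gives no distribution of use.
- That the using/free mismatch makes the inference invalid. It is a labelling fault, although a reader relying on the scoring table would read the effect backwards.

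**Conclusion.** The concern holds in this form: as written, the TLFB proportion model has no participant-level variance, so it either cannot be fitted or gives standard errors that are too small. For one month the understatement is about 1.3-fold (rho 0.02) to 4-fold (rho 0.5), with simulated type I error of 22–69% for rho 0.1–0.7. These figures rest on assumed values of rho, an assumed 60 users and a mean proportion of 0.5. For three months the 30-trial code partly offsets the error, and at rho 0.02 cancels it (0.96).

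The missing 90-day denominator and the inconsistent direction are separate, smaller faults. This should be fixed but is not critical: it concerns one secondary outcome among baseline cannabis users, and the primary PANSS analysis is unaffected.

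**What to change.** Choose one of two routes in section 5 and Appendix 1:

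1. Analyse the proportion of days using cannabis with the linear mixed model already specified for the other outcomes. The treatment effect is still a difference in proportions, which is what the identity link was meant to give.
2. Keep the binomial identity-link mean model, remove the residual structure, and use participant-clustered robust standard errors.

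In either case, state the denominator for each recall period (30 for one month, 90 for three months), give code for both, and use days using throughout so that the sign agrees with Appendix 2. Do not change 30 to 90 without also repairing the variance: on a rescaled proportion, that alone shrinks the three-month standard error by a factor of 1.73.

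The cost is SAP wording and code. The linear model is an approximation for a bounded outcome. Clustered standard errors can be liberal in a small subgroup (up to 14% in the simulation). The REML model with two timepoints was not itself simulated; the 4–7% above is for ordinary regression at one follow-up.
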